4.2.2 Secondary Endpoints and Analyses

4.2.2.1 Occurrence of pulmonary AEs, including diagnoses of events, by grade

Definition of pulmonary AE:

- Pulmonary AE is defined as pulmonary adverse event recorded in the CRF. For this study, pulmonary AE do not include pneumonitis event. An AE episode start from onset date of an AE record and stop at the date when AE is resolved. List of terms for pulmonary event can be found in section 8.3.
- Pulmonary AE at diagnosis is defined as the earliest onset of pulmonary AE on or after Day 1, or onset of subsequent AE episode after previously resolved pulmonary AE.
- Highest CTCAE grade of pulmonary AE is defined as the pulmonary AE with the highest CTCAE grade from on or after Day 1 per AE episode. Pulmonary AE with the highest grade can occur on the same date or after the earliest pulmonary AE.
- Patient with response “yes” to CRF question “Is this baseline condition suggestive of a respiratory disease?” and the condition is on-going will not be included in this analysis.

Where there are only limited number of pulmonary AE, listing will be provided including relevant dates, CTCAE grade, and duration, etc.

Where there are sufficient number of pulmonary AE, frequency and percentage (95%CI) of patients with pulmonary AE will be summarized by CTCAE grade for pulmonary AE at diagnosis, and highest CTCAE grade of pulmonary AE and by relationship with pneumonitis.

4.2.2.2 Duration (days) of pulmonary AEs by type and grade

The definition of pulmonary AE at diagnosis (excluding pneumonitis) is the same as defined section 4.2.2.1. The start and end dates of pulmonary AE duration are defined as follows:

- The onset date of each pulmonary AE will be the onset date in the CRF.
- The end date of a pulmonary AE will be the date when the AE is resolved as recorded in the CRF. The onset AE and AE with resolution could have different AE numbers.

The following censoring rules will be used:

- Death date for patient who died before AE being resolved.
- Date of study exit for patient who did not report end date of the AE or on-going beyond end of study.

The duration will be calculated as following:

Duration of a pulmonary AE = End date of pulmonary AE or date of censor – Onset date of pulmonary AE + 1

Where there are only limited number of pulmonary AE, listing will be provided as stated in section 4.2.2.1.

Where there are sufficient number of pulmonary AE, the duration will be summarized by CTCAE grade (defined as highest CTCAE grade per AE episode) using Kaplan-Meier method (Q1, median, Q3 along with 95% CI).

This analysis will be repeated for pneumonitis AEs (section 4.2.1).

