2.2 Background

The PACIFIC study was a randomized, placebo-controlled, Phase 3 trial evaluating the immune checkpoint inhibitor durvalumab in patients with unresectable Stage III NSCLC who did not have disease progression after 2 or more concurrent cycles of platinum-based chemoradiotherapy. At the first planned interim analysis, the trial showed that durvalumab treatment significantly prolonged progression-free survival, as compared with placebo, with median durations of 16.8 months (95% confidence interval [CI], 13.0 to 18.1 months) and 5.6 months (95% CI, 4.6 to 7.8 months), respectively ([Antonia et al. 2017](#)). On the basis of these results, durvalumab treatment was approved by the United States Food and Drug Administration (US FDA) for the treatment of unresectable Stage III NSCLC in patients whose disease had not progressed after platinum-based chemoradiotherapy. In addition, overall survival was found to be significantly prolonged in durvalumab-treated patients compared with the placebo group (stratified hazard ratio for death, 0.68; 99.7% CI, 0.47 to 0.997; $p=0.0025$) ([Antonia et al. 2018](#)). During the PACIFIC trial, pneumonitis or radiation pneumonitis of any grade occurred in 33.9% and 24.8% and Grade 3 or 4 pneumonitis or radiation pneumonitis occurred in 3.4% and 2.6% of durvalumab and placebo patients, respectively ([Antonia et al. 2017](#)). A total of 15.4% of patients in the durvalumab arm discontinued study drug due to AEs, compared with 9.8% in the placebo arm ([Antonia et al. 2018](#)). The most frequent AEs leading to study drug discontinuation were pneumonitis (4.8% in the durvalumab group and 2.6% in the placebo group), radiation pneumonitis (1.3% in both groups), and pneumonia (1.1% in the durvalumab group and 1.3% in the placebo group). Immune checkpoint-inhibitor-related pneumonitis is a potentially serious and life-threatening toxicity. The reported incidence of pneumonitis in studies investigating anti-programmed cell death 1/programmed cell death-ligand 1 is variable and ranges from 0% to 10%, with an overall incidence of 2.7% reported in a recent meta-analysis of 20 studies with programmed cell death 1 (PD-1) inhibition; the incidence in patients with lung cancer as the underlying diagnosis is even higher ([Nishino et al. 2016](#)).

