7.1.2 Study Period

All patients enrolled will be followed up to 12 months on durvalumab or until confirmed disease progression, permanent discontinuation of durvalumab treatment, the initiation of alternative cancer therapy, unacceptable toxic events, death, or withdrawal of consent, whichever is sooner.

At the End-of-Study visit (after 12 months of durvalumab dosing or upon withdrawal/discontinuation), information about the patient including height, weight, vital signs (temperature, heart rate, respiratory rate, and blood pressure), oxygen saturation, pulmonary-related concomitant medications and procedures, and information on AEs/SAEs (including pneumonitis), will be collected. The patient will also be prompted to take the QoL and **CCI**

A patient is considered to have completed the study when he/she has provided multiparametric data using the devices and installed application on a tablet in the Current Wearable Health Monitoring System through 12 months (or 26 cycles) of durvalumab treatment. In certain cases, a patient who does not complete all 26 cycles (i.e., durvalumab treatment prematurely discontinued due to an immune-related AE) may still be considered a study completer.

The end of study is defined as the date the last expected data will be collected.

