8.3.1.4 Reporting of AEs/SAEs on Durvalumab and Device-Related Events

The ON TRAX study is interventional in nature. Although information about past and current disease history will be collected, the study is not focused on any specific medicinal products. To participate in the study, patients will be treated with durvalumab.

Clinical practice and patient pathways should be as close as possible with routine practice.

All pulmonary AEs and other AEs will be collected regardless of causality, recorded by the study physician, and followed through final resolution (or other final outcome) during the standard of care visits. If an AE is not resolved by the end of study participation, the Investigator will determine whether to authorize additional follow-up, and will document this decision.

All pregnancies and medication errors (eg, overdose) associated with the AZ drug (durvalumab) must be promptly reported by the site physician or other site personnel quoting the study number **within 1 calendar day** of initial site awareness to the data entry site (DES) via the following e-mailbox:

CCI

In the event the secure email link is unavailable (eg, due to network issues), the following fax number should be used.

Fax number: CCI [REDACTED]

AstraZeneca will include in the documentation provided to the study physician a reminder of the importance of AE reporting. AstraZeneca representatives responsible for monitoring the study will continuously reinforce this process with the sites. Adverse Events reported will be closely monitored and evaluated in context of study continuation. A list of AEs will be forwarded to the IRB(s) at the end of the study.

Individual Case Safety Reports (ICSRs) related to any of AZ's medicinal products in the context of the present study will be treated per the company's Standard Operational Procedures.

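### The Kaplan-Meier duration of pneumonitis and pulmonary AEs censors at death, which is a competing event, and part of the censoring at study exit is driven by the AE itself

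*SAP*

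**What the plan says.** SAP 4.2.2.2 makes resolution the only event: "The end date of a pulmonary AE will be the date when the AE is resolved as recorded in the CRF". It gives two censoring rules. The first is "Death date for patient who died before AE being resolved". The second is "Date of study exit for patient who did not report end date of the AE or on-going beyond end of study". Where there are enough AEs, duration is reported as quartiles with confidence intervals "by CTCAE grade (defined as highest CTCAE grade per AE episode) using Kaplan-Meier method". With few AEs there is a listing instead, and no threshold separates the two cases. The same rules apply to the event in the primary endpoint: "This analysis will be repeated for pneumonitis AEs (section 4.2.1").

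Protocol 7.1.2 sets the length of follow-up: "All patients enrolled will be followed up to 12 months on durvalumab or until confirmed disease progression, permanent discontinuation of durvalumab treatment", and it also names unacceptable toxic events and death. AEs are collected for 30 days after the End-of-Study visit (Protocol 8.3.1.3, SAP 4.2.4.8). Beyond that, "If an AE is not resolved by the end of study participation, the Investigator will determine whether to authorize additional follow-up". The key definitions in SAP 3.1 do not define the date of study exit.

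**The concern.** Kaplan-Meier treats a censored episode as having the same future chance of resolving as the episodes still under observation. After death that chance is zero. One minus the Kaplan-Meier curve then describes resolution in a setting where nobody dies, and it will be read as the proportion of patients whose AE cleared.

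The study-exit rule has a related but separate weakness. Permanent discontinuation of durvalumab because of a pulmonary AE is itself a secondary endpoint, and it ends follow-up. The event being timed can therefore cause its own censoring. If the episodes that lead to discontinuation last longer than the rest, the upper quantiles come out too short.

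The stake is how well a secondary, descriptive summary describes the longer episodes. Protocol 4.2 says that positive secondary findings will count in the decision to move to a larger trial, so the summary has a use, though a limited one.

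**Working it through.** The documents give no duration figure, so there is nothing of the plan's own to reproduce. The fatal shares, durations and exit times below are assumptions, shown with ranges.

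**1. Death, within one grade stratum.** Assume constant hazards, a resolution median of 60 days without death (λ = ln 2/60), and a share *f* of episodes ending in death, so that the death hazard is μ = λf/(1−f).

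- SAP rule (death censored): share resolved by *t* = 1 − exp(−λt). The median is 60.0 days and Q3 is 120.0 days. By day 180 the share is 1 − 2⁻³ = 87.5%. None of these depends on *f*.
- Death competing: share resolved by *t* = (1−f)[1 − exp(−(λ+μ)t)], where λ+μ = λ/(1−f).

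| *f* | Median (days) | Q3 (days) | Resolved by day 180 |
|---|---|---|---|
| SAP rule, any *f* | 60.0 | 120.0 | 87.5% |
| 2% | 60.5 | 123.0 | 86.3% |
| 5% | 61.4 | 128.1 | 84.4% |
| 10% | 63.2 | 139.6 | 81.1% |
| 20% | 67.9 | 192.0 | 74.1% |

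Worked line for *f* = 5%: 0.95 × (1 − 2^(−3/0.95)) = 0.844, and Q3 = 57 × log₂(1/(1 − 0.75/0.95)) = 57 × log₂ 4.75 = 128.1 days.

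The direction depends on the quantity wanted. If an episode is taken to end at resolution or death, the median is 60(1−f), which is 58.8 to 48.0 days for *f* of 2% to 20%. Against that quantity the SAP rule is too long.

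**2. Grade 5 stratum.** If each episode in it ends in death, each is censored. The curve stays at 1, and Q1, median and Q3 are not estimable for any number of episodes.

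**3. How many pneumonitis cases might exit because of the AE.** Protocol 2.2 reports, for the earlier randomised trial of durvalumab, pneumonitis of any grade in 33.9% of the durvalumab arm. It gives discontinuation for "pneumonitis (4.8% in the durvalumab group and 2.6% in the placebo group), radiation pneumonitis (1.3% in both groups").

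- Discontinuation: 4.8% + 1.3% = 6.1%.
- Share of cases: 6.1/33.9 = 18%. The two figures are attributed to different reports of that trial, so this assumes that they refer to the same patients.
- In 75 patients: 75 × 0.339 = 25.4 cases and 75 × 0.061 = 4.6 discontinuations.

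**4. Effect of AE-driven exit.** Assume a median duration of 90 days in the 18% who stop and 30 days in the rest. True unresolved share: S(t) = 0.18 × 2^(−t/90) + 0.82 × 2^(−t/30), which gives a median of 35.3 and Q3 of 74.0 days.

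Suppose patients who stop exit 14 days after onset and the 30-day safety follow-up is used. They are then censored at day 44, where S(44) = 0.425. After that, Kaplan-Meier follows the remaining episodes only.

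- Median: 35.3 days, unchanged because it falls before day 44.
- Q3: 44 + 30 × log₂(0.425/0.25) = 67.0 days, against 74.0.

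Range:

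- 30% stopping, censored at day 44: median unchanged at about 40 days, Q3 71 against 86.
- 18% stopping, medians 120 to 180 days against 45 (200,000 simulated episodes per setting). Censored at day 60, the median is unchanged and Q3 is 98.7 to 100.7 against 108.8 to 117.3. Censored at day 30, the median is 48.4 to 49.7 against 51.7 to 54.5, and Q3 is 93.4 to 95.1 against 108.5 to 117.5.

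The median is therefore protected only when censoring comes after it. These figures pool the grades. Stratifying by highest grade, as the SAP does, would absorb part of the effect if grade explains the longer durations.

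**The case against.** The strongest reply is that the grade strata limit the damage. A reader might infer that fatal severe episodes will be mixed with resolved ones and produce a curve that reaches 100% resolved. The SAP does not support that. Strata use the highest grade per episode, so deaths caused by the AE belong mainly in Grade 5, where the result is not estimable instead of falsely favourable. The overstatement in Grades 1-4 comes from deaths with other causes, and the documents give no rate for those.

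A reader might also infer that the study-exit rule throws away resolution dates recorded after the End-of-Study visit. The documents do not support this either. A resolution recorded in the CRF is the end date, AE collection runs for 30 more days, and Protocol 7.1.2 defines the end of study by the last expected data. What remains is an undefined term.

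Other points also stand:

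- Administrative censoring at 12 months is valid, and a censored episode is recorded as lasting at least that long.
- Protocol 8.3.1.4 has AEs followed to final outcome at standard of care visits, which reduces truncation.
- With few events the SAP gives listings, and AEs with a fatal outcome are listed separately (SAP 4.2.4.8), so deaths stay visible.
- With about 25 cases and no censoring, sampling alone would put Q3 in the example at roughly 41 to 120 days, far wider than the 7-day shift.

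None of this makes death a valid censoring event, and no planned table places deaths beside the duration quartiles.

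**Conclusion.** The concern holds in two parts of unequal weight.

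The handling of death is a specific error of method in a stated rule. For an assumed fatal share of 2% to 20% and a 60-day resolution median, correcting it raises the median by 0.5 to 7.9 days and Q3 by 3 to 72 days. It lowers the share resolved by day 180 by 1.2 to 13.4 percentage points. The upper ends need a fatal share for which the documents give no support. The Grade 5 result needs no assumption beyond Grade 5 meaning a fatal AE.

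AE-driven exit is a secondary issue. With the safety follow-up used, the central example leaves the median alone and shortens Q3 from 74 to about 67 days. That rests on the assumed durations, the assumed exit time and the 18% share.

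The primary endpoint, the sample size and the descriptive character of the study are untouched. The correction is worth making because it is cheap.

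**What to change.** In SAP 4.2.2.2, for pulmonary AEs and for pneumonitis:

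1. Replace the Kaplan-Meier summary with the cumulative incidence of resolution, with death as a competing event (Aalen-Johansen).
2. Tabulate by grade the numbers resolved, died unresolved, and unresolved at last follow-up.
3. List Grade 5 episodes and do not summarise their duration.
4. State that the date of study exit for this analysis includes the 30-day safety follow-up, so that all recorded resolution dates are used. Align this with SAP 3.2, which notes under missing end dates that AE duration is not calculated, whereas 4.2.2.2 censors an unreported end date at study exit.
5. Add a sensitivity analysis for episodes whose follow-up ended because of the AE. Items 1 and 4 do not cure informative exit, since Aalen-Johansen also assumes that the remaining censoring is non-informative.

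The cost is a change of SAP wording, one standard procedure, one small table and one sensitivity run. The onset, resolution, death, discontinuation and exit dates are already to be collected, so little or no new data should be needed.

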4.2.2.3 Permanent discontinuation of durvalumab due to pulmonary AEs, including pneumonitis

This endpoint is fulfilled by section 4.2.4.1 patient disposition.

4.2.2.4 Early discontinuation of durvalumab treatment for any reason

This endpoint is fulfilled by section 4.2.4.1 patient disposition.

4.2.2.5 Duration (days) of durvalumab treatment

Overall and actual durations of durvalumab treatment will be reported.

Overall duration of durvalumab:

Overall duration of durvalumab is calculated using the start and stop dates of durvalumab and the intended dosing interval (2 weeks) defined as follows:

- Start date of durvalumab treatment will be date of first dose of durvalumab (Day 1) recorded in the CRF.
- End date of durvalumab treatment will be defined as the earliest of:
 - Death date for patient who died before date of study exit
 - Date of last non-zero dose administration of durvalumab plus 2 weeks minus 1.
 - Date of study exit for patient who had on-going durvalumab treatment beyond date of study exit.
- Patients are considered to be under durvalumab treatment during any interruption of any reasons. The duration will be calculated as:
- Duration of durvalumab treatment = End date of durvalumab treatment – Day 1 + 1

Actual duration of durvalumab:

Actual exposure will be calculated as the intended duration (as described above) minus the total duration of interruptions (section 4.2.2.6). The calculation of actual exposure makes no adjustment for any dose reductions that may have occurred.

Duration of durvalumab treatment will be summarized for patients in SAF using summary statistics as described in section 4.1.

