7.4.6 Durvalumab Treatment

Throughout the study, updated information on the patients' durvalumab treatment will be collected, including durvalumab start and stop date, treatment holds, interruptions, and permanent discontinuations (including reasons for each), as well as details regarding other treatments such as chemotherapy and radiation therapy (including doses and number of cycles).

Concomitant medication (including over-the-counter medication) details will also be collected. The indication for treatment must be recorded, including drug name, route, and duration of drug administration.

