3. PRIMARY AND SECONDARY VARIABLES

3.1 Key Definitions

- The term ‘baseline’ is used to collectively refer to baseline visit or Day 1
 - Baseline visit is the date of informed consent.
 - This will apply to endpoints such as QoL, vital signs, spirometry, oximetry, etc.
 - For patient where there are multiple observations before the baseline visit, last non-missing observation will be used.
 - Day 1 is the date of first dose of Durvalumab. Day 1 can be up to 2 weeks after date of informed consent or may occur on the same date.
 - This will apply to endpoints related to pneumonitis, AEs, or durvalumab.
- Change from baseline will be calculated as follows:
 - Post-baseline value minus baseline value
 - If either the baseline value or post-baseline value is missing, the change from baseline is set to “missing”.
- The last dose date is defined as the last non-missing date where a non-zero dose of durvalumab is given/administered.
- The Study Day is the day relative to the Day 1. Study day will be calculated from date on or after date of Day 1 as follows:
Study day = date of assessment – date of first dose of durvalumab +1 if the date of assessment is on and after the date of first dose of durvalumab; Otherwise, Study day = date of assessment – date of first dose of durvalumab

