4.2.2.6 Treatment interruptions, duration (days) of interruptions, and the reason for interruptions

Definition of treatment interruption:

- Short interruptions (defined as the durvalumab infusion interruption during the administration recorded in CRF in a single visit) are excluded from this analysis.
- Treatment withheld is defined as temporarily withheld of durvalumab recorded in CRF. It is possible that patients have durvalumab withheld in one visit and resumed in later visit and have multiple treatment withholds.

The duration of interruption will only include treatment withheld. Short interruption which resumed during the same visit will not be included in the calculation for duration of interruption. Start and end date of duration of interruption are defined as follows:

- Start date will be defined as the date of durvalumab withheld recorded in the CRF.
- End date will be defined as the earliest of:
 - Subsequent date of non-zero dose administration of durvalumab
 - Permanent discontinuation
 - Date of study exit
 - Death date

Since it is possible for patients to experience multiple treatment withholds/resumptions, the duration of interruption will be sum of the duration of each withheld/resumption.

The duration is calculated as:

Duration (days) of interruption = \sum (End date as described above – Start date of treatment withheld + 1)

Where there are only limited number of treatment interruptions, listing will be provided as stated in section 4.2.4.6.

Where there are sufficient number of treatment interruptions, frequency and percentage of patients with treatment withheld, reason of treatment withheld, and duration of interruption will be summarized.

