4.2.4.3 NSCLC Disease History/Respiratory Disease History

NSCLC disease history will be listed including stages at diagnosis, referral, prior to treatment and study entry, histological grade and date of diagnosis.

Prior NSCLC treatment including radiation therapy with the time since last prior radiation and chemotherapy will be listed. In the radiation therapy, regimen, anatomical site, nodal station, duration of dose (days), total number of fractions, total doses, time since last prior radiation

and time since last prior radiation by intervals (< 14 days, 14 – 28 days, 29 – 42 days, 43 – 60 days, > 60 days) will be summarized.

Duration of Dose (day) = date of last dose – date of first dose +1.

Time since last prior radiation (day) = date of last dose of prior radiation – date of Day 1.

Surgical history and relevant previous respiratory procedures collected in CRF will be also presented in the listing.

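### SAP 4.2.2.5 subtracts never-resumed hold days that fall after its own treatment end date, so actual durvalumab duration can be far too short or negative; two smaller date formulas also need correcting

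*SAP*

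**What the plan says.** Duration of durvalumab treatment is a secondary endpoint (Protocol 3.2, SAP 3.3). SAP 4.2.2.5 derives two versions of it.

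- **Overall duration** runs from Day 1 to the earliest of three dates: death, study exit if treatment is ongoing, and "Date of last non-zero dose administration of durvalumab plus 2 weeks minus 1". The section adds: "Patients are considered to be under durvalumab treatment during any interruption of any reasons".
- **Actual duration**: "Actual exposure will be calculated as the intended duration (as described above) minus the total duration of interruptions (section 4.2.2.6").

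SAP 4.2.2.6 defines the interruption. "Start date will be defined as the date of durvalumab withheld recorded in the CRF". The end is the earliest of four dates. The first is "Subsequent date of non-zero dose administration of durvalumab"; the others are permanent discontinuation, study exit and death. Each hold counts as end minus start plus 1, and the holds are summed.

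SAP 4.2.4.3 gives a further date formula: "Time since last prior radiation (day) = date of last dose of prior radiation – date of Day 1". The result is to be summarised in intervals from under 14 days to over 60 days. SAP 3.1 fixes the reference date: "Day 1 is the date of first dose of Durvalumab".

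**The concern.** The two sections use different clocks. Overall duration stops at most 13 days after the last non-zero dose. A hold with no later dose continues until discontinuation, exit or death. When such a hold starts at the next scheduled dose, all of its days lie outside the period from which they are subtracted.

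The sentence placing patients on treatment during any interruption pulls the other way. If it carried the end date through a final hold, the subtraction would be sound, but the earliest-of list does not permit that. Two programmers could follow different sentences and obtain different results. The date of permanent discontinuation, which ends such a hold, is not defined.

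The patients affected are those whose drug is held and then stopped, a group of direct interest in a study of pulmonary toxicity. SAP 4.1 also calls for the minimum, so an impossible negative value would appear in the table.

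Two lesser points concern the same kind of formula. Adding 1 to a hold that ends on a dosing day counts that day as interrupted. And radiation precedes durvalumab under the eligibility criteria, so radiation date minus Day 1 is zero or negative, while the summary intervals are positive.

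**Working it through.** The documents give no numeric result for this endpoint, so the check applies the formulas as written. The inputs are the 2-week interval and end-date list (SAP 4.2.2.5), the hold rules (SAP 4.2.2.6) and the radiation formula (SAP 4.2.4.3). All dose, hold and stop dates below are illustrative assumptions.

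**Sanity check.** 26 doses two weeks apart with no hold: last dose Day 351, end 351 + 13 = Day 364, duration 364 days. This agrees with Protocol 7.1.2, which equates 12 months with 26 cycles.

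**Never-resumed hold starting at last dose + 14.** Three doses on Days 1, 15 and 29; withheld Day 43.

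- Overall = (29 + 13) - 1 + 1 = 42
- Interruption = stop day - 43 + 1
- Actual = overall - interruption

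| Stop day | Interruption | Actual as written | Actual, hold capped at overall end | Overall / actual, end date extended to stop |
|---|---|---|---|---|
| 43 | 1 | 41 | 42 | 43 / 42 |
| 57 | 15 | 27 | 42 | 57 / 42 |
| 71 | 29 | 13 | 42 | 71 / 42 |
| 85 | 43 | -1 | 42 | 85 / 42 |
| 99 | 57 | -15 | 42 | 99 / 42 |

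For one dose (overall 14, withheld Day 15), stops 0, 14, 28, 42 and 56 days after the withheld date give 13, -1, -15, -29 and -43 as written, against 14 under either repair. For six doses (overall 84, withheld Day 85, stop Day 127), the result is 84 - 43 = 41 instead of 84.

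With *k* two-weekly doses, a hold from last dose + 14 and a stop *h* days after the withheld date, actual = 14*k* - *h* - 1. The shortfall is *h* + 1 days, and the value is negative once *h* reaches 14*k*.

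**Hold recorded earlier.** One dose, withheld Day 10, stop Day 57: 14 - 48 = -34 as written. Days 10 to 14 are properly subtracted, so the capped value is 14 - 5 = 9. The shortfall is 43 days, not the full 48-day hold.

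**Stop dated before the hold.** If the stop were recorded as the last dose date (Day 29) with the drug withheld on Day 43, the interruption is 29 - 43 + 1 = -13 and actual is 42 + 13 = 55, longer than overall.

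**Resumed hold.** Doses Days 1 and 15, withheld Day 29, resumed Day 43: overall 56, interruption 43 - 29 + 1 = 15, actual 41. Without the +1 it is 56 - 14 = 42, which matches three dosing intervals. Two resumed holds: 84 - 30 = 54 instead of 56.

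**Time since radiation.** True gaps of 10, 20, 35, 50 and 75 days should fill the five intervals one each. As written they are -10, -20, -35, -50 and -75, all below 14.

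**The case against.** The strongest case against is about reach and direction.

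- *Overall duration is correct under the end-date list.* This stands. Only the second measure is wrong, and every analysis is descriptive.
- *A hold is defined as temporary, so a direct permanent stop need not create one.* This is true of direct stops. But the discontinuation, exit and death limbs operate only when no later dose ends the hold, so never-resumed holds are plainly included.
- *The on-treatment sentence merely explains why overall duration is not reduced for holds.* That is a fair reading, and it removes the clash. It does not remove the error, because the missing cap remains.
- *The direction depends on how sites date the stop.* This stands. The understatement requires a stop on or after the withheld date. It shrinks to one day if the two coincide and reverses if the stop is dated to the last dose. That is a reason to define the date.
- *Negative values would be noticed in programming.* Probably, since they need a hold at least as long as all prior treatment (12 weeks after six doses). A moderate understatement, such as 41 instead of 84, would not stand out.
- *The +1 and the radiation sign are trivial.* They are small. The +1 is the SAP's usual inclusive count, and the positive intervals make the intended sign obvious.

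**Conclusion.** The concern holds and should be fixed. As written, actual duration is wrong for any patient whose final hold is not resumed. With a hold from last dose + 14 and a stop on or after the withheld date, it is short by the days from withheld date to stop, plus 1. It becomes negative once those days reach 14 times the number of doses.

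The number of such patients, and so the effect on the mean, cannot be derived from the documents. For scale only, each patient with a 28-day final hold lowers a mean over 75 patients by 29/75 = 0.39 days.

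Interruption duration carries the one-day excess per resumed hold, and depends on the undefined stop date for holds that are not resumed. Overall duration under the literal list, the primary pneumonitis endpoint, adverse event counts and discontinuation counts are not affected. The radiation summary would collapse into one row only if its formula were programmed literally.

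**What to change.** In SAP 4.2.2.5 and 4.2.2.6, reconcile the end-date list, the on-treatment sentence and the subtraction. The simplest route:

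- Keep the end-date list and subtract only hold days that fall between Day 1 and the overall end date.
- Report final, never-resumed holds separately.
- Limit the on-treatment sentence to holds that are resumed.

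The alternative is to extend the overall end date through a final hold. That also repairs actual duration (71 - 29 = 42 in the three-dose example) but moves overall duration from 42 to 71. Capping leaves final-hold time out of overall duration; extending puts it in. The SAP must state which applies.

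Under either route:

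- Define the permanent-discontinuation date, so that it cannot precede the hold it ends.
- Refer to overall rather than intended duration in the subtraction.
- For a hold ended by a resumed dose, use resumption date minus withheld date, without the +1.
- In SAP 4.2.4.3, define time since radiation as Day 1 minus the date of the last radiation dose.

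The cost is a few edits to the SAP text and programs. No new data are needed, because Protocol 7.4.6 already collects "durvalumab start and stop date, treatment holds, interruptions, and permanent discontinuations (including reasons for each"). These are derivation rules only and do not touch dosing. If programming is already complete, the correction can be reported as a deviation in the study report, as Protocol 9.3 provides.
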